## PASS INFORMATION:

**Title:** Evaluating the occurrence of ADVERSE events among pediatric patients exposed to intravenous lacosamide (Vimpat®) using real world data

**Protocol version:** Final approved

**Date of last version of protocol:** 18th September 2019

**EU PAS register number:** EUPAS32597.

**Active Substance:** Lacosamide (R-2-acetamido-N-benzyl-3-methoxypropionamide)

**Medicinal Product:** Vimpat

**Product reference:** EU/1/08/470/001 to 035

**Procedure Number:** Not applicable

**Marketing authorisation holder address and contact:** UCB PHARMA S.A, [name]. BELGIUM

Contact: Project Manager – Dr [REDACTED] (see next section)

**Joint Pass:** No

**Research Question and objectives:** To estimate the incidence of the selected medical events for 8 System Organ Classes (SOC) and 3 Standardized MedDRA Queries (SMQs) in pediatric patients after treatment with higher IV LCM doses, compared to pediatric patients treated with recommended initial/maintenance IV LCM dose.

**Country of study:** USA

**Author:** Dr [REDACTED] (MSc, PhD – Real World Evidence Lead, Neurology epidemiology).

## LIST OF ABBREVIATIONS

ADR	Adverse drug reaction
AE	Adverse event
AED	Antiepileptic drug
AESI	Adverse events of special interest
BRV	Brivaracetam
CDM	Common data model
CRN	Clinical Research Network
CIOMS	Council for International Organizations of Medical Sciences
CPT	Current procedural terminology
HER	Electronic health record
HCPs	Healthcare providers
HCPCS	Healthcare common procedure coding system
HIPAA	Health Insurance Portability and Accountability Act
ICD	International classification of disease
IEC	Institutional ethics committee
IRB	Institution review board
IV	Intravenous
LCM	Lacosamide
LEV	Levetiracetam
LOINC	Logical observation identifier names and codes
NDC	National drug code
OMOP	Observational medical outcomes partnership
PCORnet	Patient-Centered Clinical Research Network
SADR	Severe adverse drug reaction
SAE	Serious adverse event
SNOMED-CT	Systematized nomenclature of medicine-clinical terms
US	United States
WHO	World Health Organization

## 1 EXECUTIVE SUMMARY

### • Rationale and background

An estimated 6.8 per 1,000 insured children are affected by epilepsy (Kim et al., 2016). Off-label use of newly introduced antiepileptic drugs (AEDs) in pediatric patients provides an opportunity to assess their real world use and safety. Vimpat® (lacosamide, LCM) is indicated for the treatment of partial-onset seizures in patients 4 years of age and older. This indication is currently limited to Vimpat® oral dosage forms (Film-Coated Tablets and Oral Solution) in the USA. IV use of lacosamide in children four years and over is however authorized in EU; its benefit risk is assessed as favorable by UCB and by the EU Health Authorities. Vimpat® injection is only indicated in USA for the treatment of partial-onset seizures in adults (17 years of age and older). Vimpat® dosage in adult patients can be started with the recommended initial dosage (as monotherapy 100 mg twice daily; as adjunctive therapy 50 mg twice daily) followed by a titration regimen (increase by 50 mg twice daily every week). Alternatively, it may be initiated with a single loading dose of 200 mg. The use of a loading dose in pediatric patients has not been studied yet. The purpose of the present study is to characterize further the safety of IV LCM in a pediatric population by using available data from electronic healthcare databases.

### • Research question and objectives

#### *Primary Objective*

To estimate the incidence of the selected medical events for 8 System Organ Classes (SOC) (i.e. Cardiac disorders, Skin and subcutaneous tissue disorders, Nervous system disorders, Metabolism and nutrition disorders, Psychiatric disorders, Injury, poisoning and procedural complications, General disorders and administration site conditions, Investigations) and 3 Standardized MedDRA Queries (SMQs) (i.e. Drug reaction with eosinophilia and systemic symptoms syndrome, Severe cutaneous adverse reactions, Hypersensitivity) in pediatric patients after treatment with higher IV LCM doses, compared to pediatric patients treated with recommended initial/maintenance IV LCM dose.

#### *Secondary Objectives*

1) To estimate the incidence of specific medical events included in the above mentioned 8 System Organ Classes (SOC) and 3 Standardized MedDRA Queries (SMQs) in pediatric patients aged  $\geq 1$  month  $< 17$  years, after treatment with higher IV LCM doses, compared to pediatric patients treated with recommended initial/maintenance IV LCM dose.

2) To estimate the effect of increasing IV LCM loading dose on the incidence of select medical events for the 8 SOCs and 3 SMQ terms, and to compare the incidence of these medical events in pediatric patients treated with recommended initial/maintenance IV LCM dose.

### • Study design, including data sources

#### *Study Design*

A retrospective cohort study will be conducted using data from the PEDSnet database to achieve the study objectives. Electronic health record (EHR) data will be collected from January 2009 to December 2018. Two mutually exclusive cohorts will be identified, the first

cohort consisting of pediatric patients treated with higher than the recommended IV LCM doses, and the second (comparator) cohort comprising pediatric patients treated with recommended initial/maintenance IV LCM dose. The index date will be defined as the initiation of a new IV LCM treatment episode/receipt of a higher IV LCM dose than known maintenance dose. The exposure period will be the period between the index date (as defined above) and discontinuation of LCM. Subjects will be followed from the index date up to 30 days after discontinuing treatment with LCM or censoring, and during this time will be assessed for occurrence of described study outcomes. All subjects require a baseline period prior to the index date free of either oral or IV LCM. In the stratified assessment of increasing LCM loading dose, follow up will be from the index date up to 24 hours and 7 days after discontinuing treatment with IV LCM. Outcome ascertainment will be done in two ways, 1) data elements within the PEDSnet common data model (CDM) will be examined to identify select medical events of interest; and 2) a chart review of the EHRs for all eligible study patients will be conducted to examine unstructured, text data not captured in the CDM to identify the select medical events of interest.

Patients with status epilepticus diagnostic codes in their record will be identified from the cohort and will have their results presented separately in sub tables. They will also contribute to the main study populations. This is to fulfill commitment to examine outcomes in SE patients when exposed to lacosamide.

- **Data analysis**

For both the higher IV LCM dose cohort and recommended initial/maintenance IV LCM dose comparator cohort, counts and frequencies of AEs will be reported, also the incidence rates of the AEs and associated 95% confidence intervals (CI) will be calculated. The numerator will be the total number of patients with the outcomes identified during the follow-up period. The denominator will be patient-days. Incidence rate ratios and associated 95% confidence intervals will be calculated for each outcome to compare the incidence rates of the AEs for the higher IV LCM cohort to those for the comparator cohort. To examine the safety and tolerability of increasing intravenous LCM loading dose a stratified analysis of the incidence of the primary and secondary variables will be conducted by increasing loading dose. Stratification will be centered around UCBs proposed recommended IV LCM loading dose.

If study numbers permit, all analyses will also be stratified by 1) exposure to additional AEDs, 2) IV LCM treatment indication, 3) preexisting medical events of interest, 4) use in the intensive care unit or other hospital departments, and 5) first time IV loading dose exposure vs multiple exposures. A number of sensitivity analyses will be conducted, these will include, 1) shortening the baseline period to 6 weeks, 2) excluding patients with preexisting medical events of interest, and 3) assessment of outcome definitions to assess the impact of the case definitions on the effect estimates.

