### 5.3.3 Follow-up (post-index) period

The duration of follow-up is for a maximum of 37 days from index date.

IV LCM treatment may span several days; treatment will be considered continuous if subsequent IV LCM treatment is noted to occur within 7 days of a previous treatment. If 7 days pass without a documented iv or LCM treatment, the index exposure has ended. Follow then continues until end of follow up or until the following censoring conditions apply:

Censoring: Patients will be followed for either 37 days OR until the patient is lost to follow-up[transfer out]; OR the patient is discharged from the in-patient setting [events that occur at home are not easy to track and are not included here; outpatient setting events are also excluded as we do not know what the patient has been doing at home during routine care]; OR the patient dies; OR the patient switches to another AED instead of/or adjunct to LCM; whichever comes first.

Clarification of follow up: The purpose of the study is to evaluate iv loading dose and higher subsequent dosing risk. Some patients may receive only one iv loading dose and then transfer to oral dosing which may last some weeks in the hospital setting. In the case where a patient has just one dose of iv LCM and switches to continuous oral LCM therapy, the follow up for AE evaluation will cease after a maximum of seven days of oral therapy or until censoring occurs as above. The same applies for those exposed to one dose of iv LCM and no further LCM exposure (either oral or iv).

Patients who have more than one dose of iv LCM and then switch to oral therapy will have a maximum follow up of 37 days of follow up index date or until censoring.

Patient time is contributed until either end of follow up or censor point (in days).

Patients are only included once in this study, so if we find evidence of a further iv loading dose of LCM given 6 months later say, they do not contribute to the study.

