**Table 2 NDC codes for Lacosamide**

NDC	Description
00131181067	lacosamide 10 mg/ml injectable solution [Vimpat]
001311810	lacosamide 10mg/ml intravenous injection [Vimpat]
68842081067	lacosamide 10 mg/ml injectable solution [Vimpat]
00091181067	lacosamide 10 mg/ml injectable solution [Vimpat]

The treatment episode for IV LCM will be defined based on the prescription/dispensing information including dosage, formulation, date and time (as available in the database).

The IV LCM loading dose will be defined, where possible, as the single, initial high IV LCM dose which is followed within approximately 12 hours by a subsequent lower maintenance dose.

As we are evaluating IV LCM, which is usually administered in a hospital (inpatient) setting, it is anticipated that in most cases detailed dosage information will be recorded in the patients' medical chart with detailed information on individual IV LCM doses administered, including exact dosage data and time stamps indicating time of administration. This will enable the capture of IV LCM loading dose and the identification of subsequent episodes of IV LCM loading dose exposure.

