### **5.9.1.3 Analysis of loading dose / higher than recommended initial IV LCM dose**

To examine safety and tolerability of iv LCM administration, the analysis of the key primary and secondary variables will be stratified by loading dose and recommended dose groups, stratified by ageband ie, separate tables per age band. Risk estimates will be provided with incidence rate ratios and 95% confidence limits.

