### 5.9.4 Strength and Limitations

**Unmeasured confounding:** As the study is comparing the incidence rates of select medical events in patients who are treated with a high dose of IV lacosamide to patients who are treated with recommended dose of IV lacosamide, the major confounders are factors that impact the incidence rate of these medical events of interest. These factors include age, gender, comorbidities, and exposure to other medications which are measured. Unmeasured confounding would only occur if there was a major confounder which is not measured and thus missed from the adjusted model. However, the electronic medical records include demographic information, the medical history of the patients and any medications prescribed by the physicians. Therefore we anticipate that information on most of the confounders will be available. It is possible that there will be missing information on some comorbidities, if they are not recorded by the physicians and on medications that are either bought over counter or prescribed outside the PEDSnet healthcare network. Nevertheless, most hospitals in the PEDSNet healthcare network are large with epilepsy comprehensive care centers within the neurology departments, so we anticipate reliable background medical. We do not anticipate that there will be a disproportionate difference in the recording of the medical history data and prescription of medications in patients who are treated with high dose lacosamide and recommended lacosamide prior to the index date. Therefore, we anticipate that there will be minimal unmeasured confounding. Additionally, the analysis will be using new user design to minimize confounding by indication.

**Reduced generalizability:** The PEDSnet database is restricted to subjects seeking and receiving medical care within a facility affiliated with PEDSnet. Data is obtained from multiple care sites and type (e.g. in-patient, out-patient, emergency department). However, if a report of an event was made or a subject was treated for an event at a facility that is not affiliated PEDSnet, this information will not be captured in the PEDSnet data. However, as most events are anticipated to occur within 24 hours of receiving IV LCM, the impact of this is likely to be low.

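### The summary sets 24-hour and 7-day windows for the loading-dose assessment, section 5.9.1.3 has none, and no planned rate ratio isolates the period soon after the index dose

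*Protocol*

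**What the plan says.** The Executive Summary (Study Design) states that, for the stratified assessment of loading dose, "follow up will be from the index date up to 24 hours and 7 days after discontinuing treatment with IV LCM". Under Data analysis it adds that "a stratified analysis of the incidence of the primary and secondary variables will be conducted by increasing loading dose".

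Section 5.9.1.3, which defines that assessment, says only that "the analysis of the key primary and secondary variables will be stratified by loading dose and recommended dose groups", with separate tables by age band. It gives no time window, and no other part of 5.9 gives a 24-hour or 7-day one.

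Follow-up is set in 5.3.3: "The duration of follow-up is for a maximum of 37 days from index date". For a child who has one IV dose and then moves to oral lacosamide, "the follow up for AE evaluation will cease after a maximum of seven days of oral therapy or until censoring occurs as above"; the same limit applies if no further lacosamide is given. Censoring also occurs when "OR the patient is discharged from the in-patient setting", and at death, transfer out or the start of another AED. Section 5.9.1.4 plans one sensitivity analysis that leaves out the 30 days after IV lacosamide stops.

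On timing, 5.9.4 argues that care outside the network matters little, "as most events are anticipated to occur within 24 hours of receiving IV LCM". Section 5.9.1.2 uses a patient-day denominator and warns that such rates assume a constant hazard and need caution when events come early or late.

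**The concern.** Two current parts of the protocol disagree on whether the loading-dose assessment has acute windows. An analyst following 5.9.1.3 would produce none. An analyst following the summary would produce windows that run past the end of IV treatment.

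The protocol expects events soon after dosing, yet each rate ratio it specifies covers either the whole follow-up or the follow-up without the 30-day tail. If a higher first dose raises the rate of cardiac, nervous-system or injection-site events for a day, that excess is averaged with later inpatient days on which the two groups may not differ. The ratio then moves towards 1, and a real early effect is harder to see. This would happen even if both groups were followed for the same time.

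**Working it through.** **Nothing to reproduce.** The protocol gives no expected event rate, effect size or power. Section 5.9.3 has only a feasibility count of 875, not split by dose group. The figures below rest on stated assumptions.

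**Step 1: the anchor.** The summary's windows end 24 hours or 7 days after IV lacosamide is discontinued. For a child treated for 10 days, they close at about day 11 and day 17. Neither separates the first day from the rest of treatment, so copying the summary sentence into 5.9.1.3 would not help.

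**Step 2: dilution.** Assume equal follow-up of T days in both groups, uncommon events, a rate ratio RR on day 1 and 1 afterwards, and a comparator day-1 rate k times its later daily rate. Then

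- pooled ratio = (RR × k + T − 1) / (k + T − 1)
- share of comparator events on day 1: f = k / (k + T − 1)
- hence pooled ratio = 1 + f × (RR − 1).

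With RR = 3:

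| Setting | f | Pooled ratio |
|---|---|---|
| 24-hour window only | 1 | 3.0 |
| 37 days, uniform background (k = 1) | 1/37 = 0.027 | 39/37 = 1.05 |
| 7 days, uniform background (k = 1) | 1/7 = 0.143 | 9/7 = 1.29 |
| 37 days, k = 10 | 10/46 = 0.22 | 66/46 = 1.43 |
| 7 days, k = 10 | 10/16 = 0.63 | 36/16 = 2.25 |
| Half of comparator events on day 1 | 0.5 | 1 + 0.5 × 2 = 2.0 |
| 80% of comparator events on day 1 | 0.8 | 1 + 0.8 × 2 = 2.6 |

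For RR = 2 the uniform-background results are 1.03 (37 days) and 1.14 (7 days), and the range for f from 0.5 to 0.8 is 1.5 to 1.8. For RR = 5 they are 1.11, 1.57, and 3.0 to 4.2.

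**Step 3: what this means for detection.** As an illustration, assume 250 children per group, a comparator day-1 risk of 2%, RR = 3 and a two-sided 5% Wald test on the log ratio. Power = Φ(ln ratio / √(1/e0 + 1/e1) − 1.96), where e0 and e1 are expected events.

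- 24-hour window: e0 = 5, e1 = 15, power 57%.
- 7 days, uniform background: e0 = 35, e1 = 45, power 20%.
- Full follow-up, f = 0.5: e0 = 10, e1 = 20, power 43%.
- Full follow-up, f = 0.8: e0 = 6.25, e1 = 16.25, power 53%.

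**Step 4: date-only records.** If the 24-hour window becomes index day plus next day, a ratio of 3 with uniform background is seen as (3 + 1)/2 = 2.0.

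**The case against.** A reader might infer that an acute excess would be largely lost. The documents do not support that as a general statement. The figure of 1.05 needs a uniform background rate and 37 days of follow-up for everyone. The protocol expects most events within 24 hours. If that means day 1, f is above one half, so at least half of the excess is kept and power falls only from 57% to between 43% and 53% in the illustration. Also, 37 days is a ceiling: single-dose patients stop at about 7 days and discharge ends follow-up earlier.

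A reader might also infer that there is only one pooled window, or that an acute window was withdrawn from the primary comparison. Neither is right. Section 5.9.1.4 has an analysis without the 30-day tail. The summary's windows belong only to the loading-dose assessment; it follows the main comparison to 30 days after treatment.

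Two further points stand. Section 5.3.3 says the study also concerns higher dosing after the first dose, and the expectation in 5.9.4 refers to receiving IV lacosamide, not to the first dose. Longer follow-up therefore has a purpose, and windows counted from the index dose cannot replace it. Exact risk windows may also be left to a SAP.

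The conflict remains. The protocol itself fixes windows in one place and omits them where the assessment is defined. The 7-day cap and the sensitivity analysis shorten follow-up, but neither isolates the first day.

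**Conclusion.** The point holds as an inconsistency with a conditional cost. The summary and 5.9.1.3 must be reconciled, and the summary's anchor does not serve an acute assessment. An early excess can be diluted; how far cannot be settled from the documents, because they give neither the share of events on day 1 nor the distribution of follow-up. For an assumed day-1 ratio of 3, the range runs from 1.05 (37 days) or 1.29 (7 days) for outcomes with a steady background to 2.0 to 2.6 where 50% to 80% of comparator events fall on day 1. These figures assume no effect after day 1 and equal follow-up in both groups. The change is worth making because it resolves a contradiction and adds a result that bears directly on acute risk.

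**What to change.** In 5.9.1.3, add counts, risks and rate ratios with 95% confidence intervals by dose group, up to 24 hours and up to 7 days after the index dose, beside the full-follow-up result. Where only a date is recorded, use index day plus next day and label it so. In the Executive Summary, change the anchor from the end of IV treatment to the index dose, and align its promise of an analysis by increasing loading dose with the two-group analysis now in 5.9.1.3. Keep the full-follow-up analysis, because windows counted from the index dose do not cover later higher doses.

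The cost is two more result columns in planned tables, fewer events and wider intervals per window, and coarser timing for date-only codes. Section 5.5.4 anticipates chart records "including exact dosage data and time stamps indicating time of administration" in most cases, while times in the database are used only as available. Section 5.4.1 plans chart review for about 10% of patients, whereas 5.1 says all eligible patients. How many children will have a usable dose time should therefore be established before the 24-hour window is relied on.

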## 2 MILESTONES\*

Milestone (MCR)	Expected Planned date
Start of data collection 	January 2020
End of data collection 	April 2020
Final report of study result	June 30 th 2020
Milestone (DB)	Expected Planned date
Start of database analysis	November 2019
End of database analysis	April 2020
Final report of study result	June 30 th 2020

 Date from which data extraction starts.

 Date from which the analytical dataset is completely available. \*

The final timeline will be decided based on the final approval date of the protocol

## 3 RATIONALE AND BACKGROUND

Epilepsy affects the pediatric population with an estimated prevalence of 6.8 per 1,000 insured children (Kim et al., 2016). Newly introduced antiepileptic drugs (AEDs) may be used off-label in children with epilepsy before completion of pediatric regulatory studies, creating an opportunity to evaluate the real-world use and safety of these drugs in children to support the pediatric clinical trial program (McGinnis & Kessler; Osokogu et al., 2016).

Vimpat® (lacosamide, LCM) is an AED that selectively enhances the slow inactivation of voltage-gated sodium channels without affecting rapid inactivation (Casas-Fernandez et al., 2012). It is available as oral solution, oral tablet, and intravenous (IV) solution. It is currently approved in USA for use as oral solution, oral tablet in patients over 4 years of age and as IV solution in patients over 16 years of age as an alternative to oral administration (FDA, 2017). Vimpat® was approved on Oct 2008 and first introduced to the market in 2009. IV use of lacosamide in children over four years is however authorized in the EU; its benefit risk profile is assessed as favorable by UCB and by the EU Health Authorities. Vimpat® injection is only indicated in USA for the treatment of partial-onset seizures in adults (17 years of age and older). Vimpat® dosage in adult patients can be started with the recommended initial dosage (as monotherapy 100 mg twice daily; as adjunctive therapy 50 mg twice daily) followed by a titration regimen (increase by 50 mg twice daily every week). Alternatively, it may be initiated with a single loading dose of 200 mg. The use of a loading dose in pediatric patients has not been studied yet. The purpose of the present study is to characterize further the safety of IV LCM in a pediatric population by using available data from electronic healthcare databases.

